#### 6.4.1. Solicited Local Reactions

#### Definition

Solicited local reactions at the injection site consist of pain, tenderness, erythema/redness or induration/swelling. They are assessed by the subject in a diary and by the investigator at specific time points stated in the protocol.

Local reactions will be graded based on the criteria given in US Food and Drug Administration (FDA) Guidance for Industry 'Toxicity Grading Scale for Healthy Adult and Adolescent Volunteers Enrolled in Preventive Vaccine Clinical Trials' for 'Local Reaction to Injectable Products'. The grading of local reactions to injectable product is detailed in section 8.2.9 of the protocol. The grades are Grade 0 (Absent), Grade 1 (Mild), Grade 2 (Moderate), Grade 3 (Severe) and Grade 4 (Potentially life threatening).

The solicited local reactions will be evaluated for the following time intervals:

- Prime immunization up to day 7 (inclusive) after prime immunization
- Boost immunization up to day 7 (inclusive) after boost immunization
- Both intervals combined

The intervals will start with the date and time of the immunization.

Clarification: The interval 'prime immunization up to day 7 after prime immunization' includes study day 1 to study day 8. This applies to the other intervals accordingly.

All analyses are based on local reactions independent of their relatedness to IMP.

#### Analysis

Local reactions with missing time and occurring on the day of prime immunization will be assigned to all intervals starting with the prime immunization. Local reactions with missing time and occurring on the day of the boost immunization will be assigned to all intervals including the boost immunization. Local reactions with missing date will be assigned to each of the respective intervals if it cannot be ruled out, that it belongs to the time interval. The following analyses will be done for local reactions assessed by the subject, for local reactions assessed by the investigator and for both combined:

Differing from protocol section 9.4.2, the number and percentage of subjects reporting at least one local reaction in each time interval will be summarized for any local reaction and by worst grade.

The denominator of the percentages will be the number of subjects with any information on local reactions in the diary available in the respective time interval.

The number and percentage of subjects reporting at least one local reaction will be summarized by local reaction type (pain, tenderness, erythema/redness and induration/swelling) and by worst grade for each time interval. The denominator of the percentages will be the number of subjects with any information on local reactions in the diary available in the respective time interval.

The following analyses will be done for local reactions assessed by subjects:

Time after prime and after boost from

- First dose to first local reaction,
- First dose to first local reaction with grade >=3,
- First local reaction to last local reaction and
- First local reaction with grade >=3 to last local reaction with grade >= 3

will be summarized descriptively overall and by local reaction term.

The same variables will be analyzed for any reaction (local or systemic).

Moreover, the frequency of subjects with solicited local reactions and any solicited reactions within 7 days after each dose per day and the frequency of subjects with solicited local reactions within 7 days after each dose by term per day will be analyzed.

The compliance with the diary from each immunization up to 7 days after each immunization will be presented. Therefore, a table giving the number and percentage of subjects with any information on local reactions in the diary (overall and by local reaction term) available per day will be given. The compliance with the diary based on any information on any reaction (local or systemic) will also be given.

All local reactions from the study will be listed. Additionally, all days with information on local reactions in the diary will be listed.

For each vaccine type, local reactions assessed by subject will be presented graphically using a bar plot.

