# 9 STATISTICAL CONSIDERATIONS

# 9.1 Statistical hypotheses

There is no formal statistical hypothesis under test.

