## 6.1.1. Tables and Listings

#### Tables

In general, data will be summarized by groups (i.e., by vaccine type [BNT162a1, BNT162b1, BNT162b2, BNT162c2 SD and BNT162c2 P/B] and cohort) and all cohorts combined for each type (cohort-total). Furthermore, selected cohorts may be combined. The cohorts and cohort-total will be presented in columns and the different vaccine types in different tables.

There may be additional total columns for younger (18 to 55 years) and older (56 to 85 years) subjects.

Descriptive summary tables as well as figures will be based on scheduled visits.

Continuous variables will be summarized by group using the following descriptive statistics: number of subjects with non-missing data (n), mean, standard deviation (SD), median, minimum (min) and maximum (max).

Descriptive statistics of titer and fold increase of titer will additionally include geometric mean and its two-sided 95% confidence interval (CI). The geometric mean titer (GMT) is calculated as the mean of the logarithm of the functional antibody titers, back-transformed into the original scale. Two-sided CIs will be obtained by calculating CIs using t-distribution for the mean of the logarithmically transformed assay results and transforming the limits back to the original scale.

Geometric mean fold rise (GMFR) is calculated as the mean of the difference of logarithmically transformed assay results (post vaccination time point – pre vaccination time point) and back-transformed into the original scale. Two-sided CIs will be obtained by calculating CIs using Student's t-distribution for the mean difference of the logarithmically transformed assay results and transforming the limits back to the original scale.

Categorical variables will be summarized by group presenting absolute and relative frequencies (n and %) of subjects in each category (including the category 'missing' if applicable).

Percentages will be calculated based on the number of subjects in the respective analysis set (N) as denominator if not stated differently. Percentages may be presented with exact 95% Clopper-Pearson CIs.

SDs as well as CIs will only be calculated if values of at least 3 subjects are available.

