#### Analysis

Solicited systemic reactions will be analyzed in the same way as solicited local reactions (see Section 6.4.1 of the SAP).

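### The diary-based denominator also governs the investigator-assessed and combined reaction tables, so these additional percentages can be overstated and can exceed 100%

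*SAP*

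**What the plan says.** SAP 6.4.1 recognises two sources of reaction data: "They are assessed by the subject in a diary and by the investigator at specific time points stated in the protocol". The block of worst-grade tables is then introduced as being done "for local reactions assessed by the subject, for local reactions assessed by the investigator and for both combined". Under that lead-in the denominator is given twice, once for any local reaction and once by reaction type, both times as the "number of subjects with any information on local reactions in the diary", counted within the interval. A separate lead-in for analyses of subject-assessed reactions alone comes only after these two statements.

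The rule replaces the SAP's default in 6.1.1: "Percentages will be calculated based on the number of subjects in the respective analysis set (N) as denominator if not stated differently". No denominator based on investigator assessments, or on either source, appears anywhere. Section 6.4.2 extends the rule: "Solicited systemic reactions will be analyzed in the same way as solicited local reactions".

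SAP 6.4 limits the reach. It makes subject-assessed reactions the primary endpoint and treats the investigator's assessments as additional analyses, included so that the data are complete.

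**The concern.** A percentage is only a proportion if everyone in the numerator is also in the denominator. Here the numerator of the investigator-assessed and combined tables can draw on people whom the denominator leaves out. The investigator's assessment does not depend on the diary: the schedules in Protocol 1.3 place it on site at 1, 3 and 6 h after each dose and at later visits. A subject who wrote nothing in the diary can still have a recorded reaction.

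Investigator data are added to make the picture complete, yet the subjects for whom they add most are the ones the denominator drops. A count above the denominator would also leave the exact Clopper-Pearson interval, which SAP 6.1.1 allows, undefined.

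A second, smaller matter concerns the subject-assessed tables. Any diary information in the interval qualifies a subject as observed. The interval runs from study day 1 to study day 8, so one entry in eight days is enough.

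**Working it through.** The plan states no figure to reproduce, and the trial is descriptive ("There is no formal statistical hypothesis under test"). The check is a reading of the rule followed by illustrative arithmetic.

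**Step 1: which tables can be affected.**
- Subject-assessed: a subject with a dated diary reaction has diary information in that interval, so numerator and denominator agree. The narrow exception is a diary reaction with a missing date. SAP 6.4.1 assigns it to every interval that cannot be ruled out, which could include one where the subject has no dated entry.
- Investigator-assessed and combined: a reaction can come from a subject with no diary entry, so numerator and denominator can disagree.

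**Step 2: size of the mismatch.** Inputs are N = 12, 30 and 90, the cohort sizes in Protocol Tables 1 to 3. The number m of subjects with no diary entry in the interval and the number r of reactors are assumptions. Assume that all N subjects have at least one investigator assessment in the interval, and that the m non-diary subjects are among the r reactors.

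- SAP percentage: r/(N − m)
- Either-source percentage: r/N
- Shift: r/(N − m) − r/N = r·m/[N(N − m)]

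For N = 12 and m = 1 the shift is r/132.

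| N | m | r | SAP rule | Either source | Shift (points) |
|---|---|---|---|---|---|
| 12 | 1 | 1 | 1/11 = 9.1% | 1/12 = 8.3% | 0.8 |
| 12 | 1 | 6 | 6/11 = 54.5% | 6/12 = 50.0% | 4.5 |
| 12 | 1 | 12 | 12/11 = 109.1% | 12/12 = 100.0% | 9.1 |
| 12 | 3 | 10 | 10/9 = 111.1% | 10/12 = 83.3% | 27.8 |
| 30 | 1 | 15 | 15/29 = 51.7% | 15/30 = 50.0% | 1.7 |
| 90 | 1 | 45 | 45/89 = 50.6% | 45/90 = 50.0% | 0.6 |

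With m = 0 the shift is zero in every row. In the investigator-assessed table the error can also run the other way: a subject with a diary but no investigator assessment makes the denominator too large.

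**Step 3: short diaries in the subject-assessed tables.** SAP 6.1.3 does not impute missing data. A subject whose only entry is reaction-free therefore counts as having had no reaction in the whole interval. For the two intervals combined, an entry after either dose is enough. Let p be the true incidence over the interval, k the number of subjects with one diary day, and c the share of reactors whom that one day would catch. The expected percentage is p·[(N − k) + k·c]/N. With p = 60% and c from 1/8 to 1/2, all assumed:

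- N = 12, k = 1: 0.60 × 11.125/12 = 55.6% to 0.60 × 11.5/12 = 57.5%
- N = 12, k = 3: 0.60 × 9.375/12 = 46.9% to 0.60 × 10.5/12 = 52.5%
- N = 30, k = 3: 0.60 × 27.375/30 = 54.8% to 0.60 × 28.5/30 = 57.0%

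The two effects have different targets: Step 2 concerns the additional tables, Step 3 the primary ones.

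**The case against.** The strongest reply is that this is a gap in wording around secondary output. SAP 6.4 keeps the investigator's data out of the primary endpoint. The SAP does not actually say that a subject outside the denominator is to be counted in the numerator, and a careful programmer might restrict both. Missing a diary altogether should be uncommon: in the dose-ranging prime/boost schedule, diaries are issued at Visit 1 and collected at Visit 2, at the 48 h contact and at Visit 3. For the short-diary point, SAP 6.4.1 already plans a per-day table of diary completeness, reaction frequencies by day, and a listing of every day with diary information. Protocol 2.3.1 also says that events of this kind typically begin within 24 h of immunization, so a single early entry may catch most of them.

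Most of this stands, and it limits reach and size. It does not settle the point. Restricting the numerator to diary subjects would discard the very reactions that the investigator tables were added to capture, and the text asks for neither solution. The completeness tables disclose short diaries but leave the percentages as they are.

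Three stronger readings might be inferred, and the documents support none of them.
- That the primary percentages can exceed 100% through investigator data. They cannot, because those data are not in the primary tables.
- That the additional percentages are in fact overstated. This requires at least one dosed subject without a diary entry, and no rate is given.
- That each missing diary moves a cohort of 12 by 8 to 10 points. With one missing diary, 8 points needs at least 11 reactors (11/132 = 8.3 points); sparse rows, such as severe grades, hardly move.

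**Conclusion.** The point holds for the investigator-assessed and combined tables, local and systemic. As written, the denominator does not match the numerator, and the percentages can be overstated and can exceed 100%. The size rests on an assumed number of subjects without a diary entry. For one such subject it ranges from under 1 to about 9 points in a cohort of 12; at about 50% incidence it is 1.7 points in a cohort of 30 and 0.6 in a cohort of 90. No hypothesis test or primary percentage depends on it, apart from the narrow missing-date case.

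The short-diary point is secondary. It does reach the primary tables, but it understates incidence only where the missing days held a subject's only or worst reaction. How often that happens cannot be judged from the documents.

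**What to change.** Replace the single denominator in SAP 6.4.1 with one per source, applying through 6.4.2 to systemic reactions:
- subject-assessed tables: subjects with any diary information in the interval, as now;
- investigator-assessed tables: subjects with at least one investigator assessment in the interval;
- combined tables: subjects with information from either source in the interval.

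For the subject-assessed tables, add a supportive row restricted to subjects with a complete or near-complete 7-day diary, with the minimum number of days stated in advance.

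The cost is a sentence or two in the SAP and a program change. All the data are already collected.

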#### Safety Set (SAF)

The safety set is defined as all subjects who received at least one dose of Investigational Medicinal Product (IMP).

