#### 6.1.3. Missing Data

As a general rule, missing data will not be substituted (i.e., missing data will not be replaced but will be handled as "missing" in the statistical evaluation), with the following exception for summary analyses:

Clinical safety laboratory variables given as '<xx' will be evaluated as 0.5 \* xx in the summary tables. In the listings they will be displayed as "<xx" or similar.

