## 6.4. Primary Analyses

Hereinafter, the primary analyses for Part A are described.

The primary endpoints are solicited local reactions at the injection site, solicited systemic reactions and the proportion of subjects with at least 1 unsolicited treatment emergent adverse event (TEAE).

Clarification: Only local and systemic reactions assessed by subject will be analysed as primary endpoint. As additional analyses, the local and systemic reactions assessed by the investigator will also be included in tables displaying "worst possible grade" for data completeness.

All primary analyses will be performed using the SAF and analyses of adverse events will possibly be repeated using the SAFB.

All primary analysis endpoints will be summarized by group (i.e. by vaccine type and cohort) and all cohorts combined for each type (cohort-total).

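### The per-day solicited-reaction frequencies have no stated denominator, so the Safety Set default keeps subjects with no diary entry that day, and subjects never boosted, in every daily percentage

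*SAP*

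**What the plan says.** The general rule is in SAP 6.1.1, Tables: "Percentages will be calculated based on the number of subjects in the respective analysis set (N) as denominator if not stated differently". SAP 6.4 names the set for the solicited-reaction endpoints: "All primary analyses will be performed using the SAF and analyses of adverse events will possibly be repeated using the SAFB". The Safety Set (SAF) requires neither a diary nor a boost: "The safety set is defined as all subjects who received at least one dose of Investigational Medicinal Product (IMP").

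SAP 6.4.1 departs from the default twice, once for the table of any reaction by worst grade and once for the table by reaction type and worst grade. In both places the rule, tied to the interval being tabulated, is "The denominator of the percentages will be the number of subjects with any information on local reactions in the diary available in the respective time".

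The daily frequencies come later in 6.4.1, under a separate lead-in for subject-assessed reactions: "the frequency of subjects with solicited local reactions within 7 days after each dose by term per day will be analyzed". The same sentence covers any local reaction and any solicited reaction per day. No denominator is given there. SAP 6.4.2 sends systemic reactions through the same analysis.

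Three other provisions bear on the point. SAP 6.1.1 describes categorical summaries as "presenting absolute and relative frequencies (n and %) of subjects in each category (including the category 'missing' if applicable"). SAP 6.1.3 says that "missing data will not be replaced but will be handled as 'missing' in the statistical evaluation". SAP 6.4.1 also plans a compliance table with the "number and percentage of subjects with any information on local reactions in the diary (overall and by local reaction term) available per day".

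**The concern.** A subject-assessed reaction on a given day can be seen only if the diary has an entry for that day, and a post-boost reaction can occur only if the boost was given. With N of the SAF as denominator, subjects who fail either condition are counted below the line and can never be counted above it.

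Subject-assessed solicited reactions are a primary endpoint, and the daily table shows how they rise and fall over the week after each dose. If diary completion drops during that week, part of the apparent decline may be loss of entries rather than resolution. After the boost, a cohort that received no second dose would show no reactions, which can be read as good tolerability.

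**Working it through.** The plan states no figure on this point, so there is nothing to reproduce. The check is which rule governs and what it does.

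**1. Governing rule.** The default in 6.1.1 yields only to a stated alternative. In 6.4.1 the stated alternative belongs to the two interval tables. Where the SAP wants an available-data denominator elsewhere, it says so, as in 6.5.3 for seroconversion. The daily frequencies therefore take N of the SAF. A 'missing' row, or the rule against replacing missing values, makes absent entries visible but does not take those subjects out of N.

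**2. Formula.** Let N be the SAF count, m the subjects with an entry that day, and r those reporting the reaction. Then

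r/N = (m/N) × (r/m).

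**3. Missing entries (completion is assumed, because the documents give none).** With a 50% rate among subjects with an entry:

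| Completion m/N | Daily percentage over N |
|---|---|
| 100% | 50% |
| 90% | 45% |
| 80% | 40% |
| 75% | 37.5% |

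In a cohort of 12 with m = 10 and r = 5, the two denominators give 5/10 = 50.0% and 5/12 = 41.7%. If completion fell from 95% to 80% over the week, a constant rate would appear to fall by 1 − 0.80/0.95 = 16%.

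**4. Carrying the interval denominator over would not settle it.** Take 12 in the SAF, 11 with any entry in the interval, 9 with an entry that day and 6 reactions. The rate is 6/12 = 50.0%, 6/11 = 54.5% or 6/9 = 66.7%.

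**5. What can be said about direction.** In the same example 3 of the 12 have no entry that day. If all three were symptom-free, the rate in the 12 is 6/12 = 50%. If all three had the reaction, it is 9/12 = 75%. So r/N is the lower limit, and it is exactly right when every skipped day was symptom-free. The factor m/N measures the bias only if skipping is unrelated to symptoms.

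**6. Boost not given (no completion assumption).**
- BNT162b1: the note to protocol Table 2 says the boost was not given at 60 µg. Protocol Table 5 gives a maximum of 120 subjects in 10 cohorts, and Table 1 plans 12 per cohort. At those numbers at most 120 − 12 = 108 can have a post-boost entry, and 108/120 = 0.90. Rates of 25%, 50% and 75% show as at most 22.5%, 45% and 67.5% in the cohort-total. With an assumed 90% completion among boosted subjects, the factor is 0.90 × 0.90 = 0.81. The 60 µg column itself shows 0/12 = 0% on every post-boost day.
- BNT162a1: note b to protocol Table 1 says six subjects received the 3 µg prime and Day 22 dosing was not performed. That column shows 0/6 = 0%. If the other five listed cohorts were filled with 12 each, the cohort-total factor is 60/66 = 0.91. Protocol Table 1 also says further BNT162a1 dosing is deferred, so with fewer cohorts the factor is lower.

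**The case against.** The strongest reply is that this is a drafting omission. The section twice uses diary-based denominators, the version history records a changed denominator for the reaction tables without limiting it to some of them, and the output shells are not in the SAP. A programmer might well use the diary count, and might read days after each dose as applying only to subjects who received that dose. That is plausible, but it is not written, and the written default says otherwise. The Safety Boost Set does not help: the SAP uses it only to repeat adverse-event analyses.

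Several other points stand.
- A reader might infer that the plan records missing diary days as symptom-free. It does not: nothing is imputed, and a 'missing' row may appear.
- A reader might also infer that daily rates are known to be too low by the completion factor. The documents do not support that. They give no completion figures. Protocol 8.2.8 asks subjects to record any reactions between visits, which could lead some to skip symptom-free days, although protocol 8.2.13 describes daily reports.
- The daily table is not the only account of onset and resolution. SAP 6.4.1 also summarizes time to first reaction and time from first to last reaction, and these do not use N as denominator.
- The interval tables, which match the protocol's primary endpoints, already have a diary-based denominator.
- The compliance table would let a careful reader rescale the daily figures.

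**Conclusion.** The gap is real and should be closed, but it is limited to descriptive daily frequencies. As written, each daily percentage is the rate among subjects with an entry multiplied by that day's share of the SAF with an entry.

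For the prime dose the effect is zero with complete diaries and otherwise of unknown size. Treating it as a bias of size m/N requires that skipped entries be unrelated to symptoms.

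After the boost the defect does not depend on completion. Cohorts with no boost would show 0% on days when there was no dose to react to, and the cohort-total is diluted. The factor 0.90 for BNT162b1 rests on the planned maximum, with all ten cohorts run and 12 subjects primed at 60 µg. It would be lower if other cohorts were not run, and higher if fewer received the 60 µg prime. It applies to the cohort-total and does not alter the columns of boosted BNT162b1 cohorts.

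**What to change.** Add to SAP 6.4.1, and by reference to 6.4.2: for each per-day frequency, the denominator is the number of subjects with diary information for that reaction term (or for any reaction, in the overall rows) on that day after the respective dose; post-boost days include only subjects who received the boost. Show cohorts with no boosted subjects as not applicable rather than 0%.

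The cost is one SAP statement and a small programming change, since the daily counts overall and by term are already produced for the compliance table.

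There are two downsides. The denominator will vary by day, and the rates could be somewhat too high if subjects skip entries mainly on symptom-free days. For that reason, print the number with the reaction, the number with an entry and N side by side, so that both ratios can be read.
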